4.8 Deviation from Inclusion/Exclusion Criteria

Deviation from the inclusion or exclusion criteria will not be allowed. If deviation of inclusion/exclusion criteria is discovered after randomization, the investigator should contact the medical monitor for discussion. A decision will be made whether to allow a patient to continue or withdrawal from the study medication.

See [Section 6.8](#) for additional details.

4.8.1 Patient Withdrawal and Replacement

See [Section 5.5](#) for reasons for removal from the trial. Withdrawn patients may be replaced during the MAD part of the study after discussion between the principal investigator or designee and sponsor.

5 STUDY PROCEDURES

Refer to the eCRF completion guidelines for data collection requirements and documentation of study assessments/procedures.

5.1 Screening

Screening will be the same for both the MAD and POC portions of the study.

Screening will take place from Day -28 to Day -1, and assessments may be performed over more than 1 visit. Confirmation that the most current IRB/IEC approved informed consent form (ICF) has been signed must occur before any study-specific screening procedures are performed. Procedures that are part of standard of care are not considered study-specific procedures and may be performed prior to informed consent and used to determine eligibility.

All screened patients will be assigned a unique screening number. The screening number will include a 3-digit site number and a 4-digit sequential number to identify patients from the time of screening. Only eligible patients who are confirmed by central review as meeting the inclusion/exclusion criteria, listed in [Section 4.4](#) and [Section 4.5](#) respectively, will be enrolled in the study. Screened patients who drop out of the clinical study before randomization will be recorded as screen failures. If rescreening occurs, the site will assign a new screening number.

Specific procedures at the screening visit will include:

- Medical history documentation
- Review of inclusion and exclusion criteria
 - Patient medical records must contain documentation of SLE diagnosis
 - C-SSRS
- Concomitant medication documentation
- Demographics
- Full physical examination
- Vital signs
- Chest x-ray (a prior x-ray can be used if taken within 12 weeks of screening date)
- Laboratory evaluations (non-fasting):
 - Hematology and clinical chemistry
 - Serology (Hepatitis B and C; HIV-1/2 combination)
 - TB test

- CRP
- Direct Coomb's test (if indicated for hemolytic anemia)
- CD4+ count, total IgG and IgM levels, plasma CCI [REDACTED], CCI [REDACTED]
- Serum pregnancy test (WOCBP)
- FSH (postmenopausal women under age 55 years)
- Spot urine for protein/creatinine ratio
- Urinalysis
- Stool sample
- 12-lead ECG
- SLE-related indices (BILAG-2004 Index, SLEDAI-2K, ACR-28 joint count, CLASI, Physician's Global Assessment (PGA) of disease activity)

Screening procedures are listed in the Schedule of Assessments ([Section 3.4](#)), and details are provided in [Section 6](#).

5.1.1 Retesting During Screening Period

A single retesting of laboratory parameters and/or other assessments during the screening period is permitted (in addition to any parameters that require a confirmatory value) only if:

- medically indicated
- there is evidence a laboratory sample was mislabeled, indeterminate, inadequately processed, and/or deteriorated in transit to the central laboratory

Any new result will override the previous result (ie, the most current result prior to randomization) and is the value by which study inclusion/exclusion will be assessed, as it represents the patient's most current clinical state. This will also apply to patients who are being rescreened.

5.2 Enrollment/Randomization and Day 0 Treatment

Randomization should occur after patient eligibility for enrollment has been confirmed by the central eligibility review.

Prior to randomization, the study site should confirm that the patient still meets inclusion/exclusion criteria (especially SLE disease activity and treatment). The site will obtain a randomization number when registering the patient in IWRS. All patients will receive BOS161721 or placebo according to the kit number assigned by the IWRS randomization scheme.

After randomization, procedures include:

- PROs: CCI [REDACTED]
- C-SSRS
- Laboratory evaluations (fasting):

- Hematology and clinical chemistry
- Direct Coomb's test (if indicated for hemolytic anemia)
- CD4+ count, total IgG and IgM levels, plasma CCI, plasma CCI and CCI whole blood for leukocyte immunophenotype
- ADA
- pSTAT3 (predose [trough] samples only in Phase 1b)
- CCI
- CCI
- CCI
- See Table 1 and Table 2 for details of PK sampling in the MAD and POC portions
- Urine pregnancy test will be collected on WOCBP prior to study drug administration
- Spot urine for protein/creatinine ratio
- Urinalysis
- Concomitant medication documentation
- Documentation of AEs and SAEs (see Section 6.2.2.5 on SAE reporting requirements)
- Full physical examination
- Vital signs (prior to PK blood draw, predose, and at 1 and 2 hours postdose on Day 0)
- 12-lead ECG (prior to PK blood draw)
- SLE-related indices (BILAG-2004 Index, SLEDAI-2K, ACR-28 joint count, CLASI, PGA)
- SLICC/ACR damage index
- Study drug administration:
 - Administration of BOS161721 or placebo will take place on-site, and is discussed in Section 7.3
- Injection site reaction assessment performed at 2 hours postdose

Procedures on Day 0 are listed in the Schedule of Assessments (Section 3.4), and details are provided in Section 6.

All patients who are enrolled, randomized, and receive study drug, or undergo study-specific procedures should re consent with any updated versions of IRB/IEC approved informed consents during study participation as applicable and per institutional guidelines.

5.3 Treatment Period/Follow-Up Visits

The following procedures will be performed as indicated in the Schedule of Assessments (Table 1 and Table 2). See Schedule of Assessment tables for allowable windows for each visit.

- Targeted physical examination
- Vital signs (prior to PK blood draw)
- Concomitant medication documentation
- Documentation of AEs and SAEs (see Section 6.2.2.5 on SAE reporting requirements)
- PROs: CCI

- Urine pregnancy tests will be collected on WOCBP prior to study drug administration
- Injection site reaction assessments will be performed predose
- Direct Coomb's test (if indicated for hemolytic anemia)
- Spot urine for protein to creatinine ratio
- Urinalysis
- CCI [REDACTED]
- Plasma CCI [REDACTED]
- PGA, BILAG-2004 Index, SLEDAI-2K, ACR-28 joint count, and the CLASI will be completed
- SLICC/ACR Damage Index will be completed at Day 180
- C-SSRS
- ECGs prior to PK blood draw
- See [Table 1](#) and [Table 2](#) for details of PK sampling in the MAD and POC studies, respectively
- Fasting hematology and chemistry assessments
- The CD4+ count and total IgG and IgM levels
- Plasma CCI [REDACTED] & CCI [REDACTED], ADA, and whole blood for leukocyte immunophenotype
- pSTAT3 (predose [trough] samples only Phase 1b)
- nAb will be analyzed by central lab if patient is positive for ADA
- CRP
- CCI [REDACTED]

5.4 Safety Follow-Up Visits

Safety follow-up visits will take place at Days 210, 240, and 270. These visits will include the following assessments as indicated in the Schedule of Assessments (Table 1 and Table 2):

- PROs: CCI [REDACTED]
- Documentation of AEs and SAEs (see [Section 6.2.2.5](#) on SAE reporting requirements)
- Injection site reactions
- Targeted physical examination
- Vital signs (prior to PK blood draw)
- Spot urine for protein/creatinine ratio and urinalysis
- Concomitant medication documentation
- BILAG-2004 Index, SLEDAI-2K, ACR-28 joint count, CLASI, and PGA
- Fasting clinical laboratory assessments (hematology and clinical chemistry)
- Direct Coomb's test (if indicated for hemolytic anemia)
- Plasma CCI [REDACTED]
- CCI [REDACTED]
- 12-lead ECG (prior to PK blood draw)

- CRP
- ADA
- CCI
- Urine pregnancy test
- See [Table 1](#) and [Table 2](#) for details of PK sampling in the MAD and POC portions, respectively

5.5 Premature Discontinuation

While patients are encouraged to complete all study evaluations, they may withdraw from the study at any time and for any reason. Every effort will be made to determine why any patient withdraws from the study prematurely. If the patient is unreachable by telephone, a registered letter, at the minimum, should be sent to the patient requesting him/her to contact the clinic.

All patients who withdraw from the study with an ongoing AE or SAE must be followed until the end of study or until the event is resolved or deemed stable, respectively.

If a patient withdraws prematurely after dosing, an end of treatment (EOT) visit should be performed (Day 180) and a last follow-up visit 90 days after dosing should be scheduled (Day 270). Safety follow-up visit procedures based on the Schedule of Assessments (see [Section 5.4](#)).

Patient participation may be terminated prior to completing the study and the reason recorded as follows:

- AE/SAE
- Protocol deviation
- Lost to follow-up
- Patient withdraws consent at their own request
- Investigator decision
- Decision by sponsor (other than AE/SAE, protocol deviation, or lost to follow-up)

Withdrawn patients may be replaced after discussion between the investigator or designee and sponsor.

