2.2 Phase 2 Proof of Concept

OBJECTIVES	ENDPOINTS
Primary	

 To demonstrate a superior effect of BOS161721 at the chosen dose compared with placebo for response on the SRI-4 	Primary Efficacy Endpoint 
 The proportion of patients with a SRI-4 response at Day 210 (see Section 6.3.4.1)
Secondary	
To demonstrate a superior effect of BOS161721 at the chosen dose compared with placebo for response on clinical indicators of SLE activity, in adult patients with moderately to severely active SLE on limited background standard of care treatment	Secondary Efficacy Endpoints 
 The proportion of patients with: 
 SRI-4 response at each visit SRI-5 and SRI-6 response at each visit (Section 6.3.4.2) a sustained reduction of oral corticosteroid (CS) (≤ 10 mg/day and \leq Day 0 dose) between Day 120 and Day 210 new BILAG A flare or > 1 BILAG B flares relative to baseline through Day 210 PGA worsening a BICLA response a CLASI response medication failures Results and changes from baseline in: 
 CLASI swollen and tender joints ACR-28 SLEDAI-2K SLICC/ACR damage index Time to medication failure Duration of longest SRI-4 response Time to first SRI-4 response Time to BILAG A flare or > 1 BILAG B flare compared to baseline through Day 210
Safety	

 To assess safety and tolerability of repeat doses of BOS161721 at the chosen dose administered SC in adult patients with moderately to severely active SLE on limited background standard of care treatment 	Safety Endpoints 
 Incidence and severity of adverse events (AEs) and serious adverse events (SAEs), related AEs, AEs leading to study drug discontinuation, AEs by severity and relatedness Injection site reactions C-SSRS 12-lead ECGs parameter results at each visit and change from baseline Vital signs (blood pressure [BP], heart rate, and temperature) parameter results at each visit and change from baseline Clinical laboratory results and change from baseline Physical examinations changes from baseline ADAs Study drug exposure/compliance

Exploratory

• CCI [REDACTED]	
• CCI [REDACTED]

• CCI [REDACTED]	
• CCI [REDACTED]

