3.5 End of Study

End of Study (Individual Patient): A patient is considered at the end of study if he/she has withdrawn, prematurely discontinued, or completed all of the study procedures including the last visit.

End of Study (End of trial): The end of the study is defined as the date of the last visit of the last patient in the study globally, or the date of which the last patient withdraws or discontinues if all prior enrolled patients have already completed/withdrawn.

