6.2.1.1 Pregnancy testing

For WOCBP, a serum pregnancy test will be performed at screening. Following a negative serum pregnancy result at screening, appropriate contraception must be commenced or continued and a further negative urine pregnancy test results will then be required at the baseline visit before the patient may receive the investigational product. Urine pregnancy tests will also be routinely repeated at study drug administration visits prior to study drug administration, at the last follow up visit day (Day 270) and additionally whenever 1 menstrual cycle is missed or when potential pregnancy is otherwise suspected. In the case of a positive pregnancy test or confirmed pregnancy, the patient will be discontinued from study drug, an EOT visit should be performed (Day 180), and a last follow-up visit 90 days after last dose should be scheduled (Day 270). Safety follow-up visit procedures (see [Section 5.4](#)) are specified in the Schedule of Assessments (see [Section 3.4](#)).

See [Section 6.2.2.7.1](#) for information on reporting of pregnancies as AEs/SAEs during the study.

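### After an early stop of study drug the protocol names no Day 210 efficacy visit, and its fixed visit-day labels fit only a patient dosed through Day 180

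*Protocol*

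**What the plan says.** The Phase 2 primary endpoint (Protocol Section 2.2) is "The proportion of patients with a SRI-4 response at Day 210". Section 8.2.3 fills missing values by LOCF and counts medication failures as non-responders.

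For early stops, Section 5.5 reads "If a patient withdraws prematurely after dosing, an end of treatment (EOT) visit should be performed (Day 180", followed by "a last follow-up visit 90 days after dosing should be scheduled (Day 270". A fragment then points to Section 5.4: "Safety follow-up visit procedures based on the Schedule of Assessments". The section opens more softly: "patients are encouraged to complete all study evaluations".

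Section 6.2.1.1 gives the same two visits, with the same labels, to a patient with a positive pregnancy test: "the patient will be discontinued from study drug, an EOT visit should be performed (Day 180". Section 3.5 says: "A patient is considered at the end of study if he/she has withdrawn, prematurely discontinued, or completed all of the study procedures".

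Section 5.4 places the safety follow-up visits at Days 210, 240 and 270 and collects BILAG, SLEDAI-2K and PGA at them. Other drug stops are required in Sections 6.2.2.6.1 (severe allergic reaction) and 6.2.2.6.3 (liver criteria), and are possible under Section 4.8 (eligibility deviation found after randomization). None of these three says what happens to the remaining visits.

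**The concern.** A patient can stop study drug and still be willing to attend. The protocol has no separate status for that patient. The one schedule it offers after an early stop has two visits, and neither is the Day 210 assessment on which the primary endpoint rests.

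This is a matter of data collection, before any question of analysis. An analysis plan can choose analysis windows and imputation methods, but it cannot supply an assessment that was not scheduled. Patients who stop for adverse events or by investigator decision may differ between arms. For them an earlier SRI-4 status, possibly months old, would stand in for Day 210. The two day labels also conflict with the timing rule beside them, so sites have no consistent instruction on when to see these patients.

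**Working it through.** **1. Where the 90-day visit falls.** Inputs: dosing on Days 0, 30, 60, 90, 120, 150 and 180 (Section 3.1.2.2), a last visit 90 days after dosing (Sections 5.5 and 6.2.1.1), and a Day 210 window of ±3 days (Table 2). Nominal visit day = last dose day + 90.

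| Last dose | 90-day visit | Within Day 210 ± 3? | Day 270 label correct? |
|---|---|---|---|
| Day 0 | Day 90 | no | no |
| Day 30 | Day 120 | no | no |
| Day 60 | Day 150 | no | no |
| Day 90 | Day 180 | no | no |
| Day 120 | Day 210 | yes | no |
| Day 150 | Day 240 | no | no |
| Day 180 | Day 270 | no | yes |

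Of the six early-stop patterns (last dose on Days 0 to 150), five miss Day 210. The Day 270 label is right only after a last dose on Day 180, the final planned dose. The Day 180 label on the EOT visit likewise fits only a patient treated to the end of the schedule.

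**2. Who is covered.** Section 5.5 is written for a patient who withdraws, but its title is premature discontinuation, and consent withdrawal is one of its six listed reasons. Section 6.2.1.1 expressly applies the two-visit rule to a drug stop. Sections 4.8, 6.2.2.6.1 and 6.2.2.6.3 are silent on visits. So the rule is explicit for pregnancy and ambiguous for the other drug stops.

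**3. Does the pointer to Section 5.4 restore Day 210?** Not clearly. It is an incomplete sentence about procedures. After a last dose on Day 0, 30, 60 or 90, a Day 210 visit would come later than the visit that Section 5.5 calls the last one.

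**4. The stated power.** Inputs from Section 8.1: 132 patients at 2:1 (88 and 44), 65% against 40%, two-sided 10%, Pearson chi-squared.

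- Pooled rate: (0.65 × 88 + 0.40 × 44)/132 = 0.567
- Standard error under no difference: √[0.567 × 0.433 × (1/88 + 1/44)] = 0.0915
- Standard error under the alternative: √[0.65 × 0.35/88 + 0.40 × 0.60/44] = 0.0897
- Power = Φ[(0.25 − 1.645 × 0.0915)/0.0897] = Φ(1.11) = 86.6%

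Exact binomial enumeration gives 86.3%. Both agree with the stated figure of more than 80%.

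**5. How many patients.** Section 8.1 places all 24 assumed dropouts (156 − 24 = 132) before entry to the FAS, so the protocol gives no rate for later discontinuation. Assuming 10-20%: 0.10 × 132 = 13 and 0.20 × 132 = 26. This is an upper count. True withdrawals, last doses on Day 120 and medication failures all come off it.

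**The case against.** The strongest reply is that Section 5.5 concerns patients who leave the study, whom no schedule can measure; that it encourages completion of all evaluations and refers to Section 5.4, where Day 210 is listed; and that the sections on allergic and hepatic stops cancel no visit. This stands in part. It shows that the text is ambiguous for those drug stops, and that some missing values could not be recovered under any schedule. It does not answer the pregnancy rule or the label contradiction, and the encouragement has no schedule attached to it.

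A reader might infer more than the documents support:

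- **That Day 210 is never measured after an early stop.** A last dose on Day 120 puts the 90-day visit on Day 210, with all SRI-4 components collected under Section 5.4.
- **That early assessments are stored or analysed under the wrong day.** No mapping rule is stated. The label may only identify which column of procedures to perform, and windows by actual day can be set in the SAP.
- **That the result could swing by about 31 points.** At an assumed 15% missing, 13/88 + 7/44 = 14.8 + 15.9 = 30.7 points. That is the gap between two extreme allocations of the missing outcomes. It ignores the medication-failure rule and observed Day 120 stops, and includes withdrawals that no schedule could recover.
- **That the trial is underpowered.** Section 8.1 states its 65% and 40% as rates with carry-forward and the non-responder rule already applied, so the power figure stands.

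The protocol also allows other imputation as sensitivity analysis (Section 8.2.3) and commits to assessing discontinuation and withdrawal (Section 8). Those steps help interpretation but do not replace an observed Day 210 value.

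**Conclusion.** The point holds in a limited form. Sections 3.5, 5.5 and 6.2.1.1 do not distinguish stopping drug from leaving the study, and no Day 210 efficacy visit is named after an early stop. This is explicit for pregnancy and unclear for the other drug stops. The Day 180 and Day 270 labels are wrong as written for anyone whose last dose came before Day 180.

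The consequence is avoidable reliance on LOCF for the primary endpoint. Its extent depends on an assumed discontinuation rate: at most about 13-26 of 132 patients at 10-20%, and fewer after the exclusions above. The documents support neither a direction nor a size of bias. Sample size and stated power are unchanged.

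**What to change.** Reconcile Sections 3.5, 5.4, 5.5 and 6.2.1.1 in one amendment:

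- Define study drug discontinuation separately from study withdrawal, and say which of them ends study participation under Section 3.5.
- Have patients who stop drug but have not withdrawn consent keep the existing Table 2 efficacy and safety assessments, without dosing, through at least Day 210. State that this applies to stops under Sections 4.8, 6.2.1.1, 6.2.2.6.1 and 6.2.2.6.3.
- Record true early terminations at their actual study day, and remove the fixed Day 180 and Day 270 labels.

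No dose or stopping criterion changes, and no patients are added. The cost is an amendment, an eCRF visit label, and some additional off-drug visits for patients already enrolled, each with its scheduled assessments.

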6 ASSESSMENTS

Every effort should be made to ensure that the protocol required tests and procedures are completed as described. However, it is anticipated that from time to time there may be circumstances, outside of the control of the investigator, which may make it unfeasible to perform the test. In these cases, the investigator will take all steps necessary to ensure the safety and wellbeing of the patient. When a protocol required test cannot be performed the investigator will document the reason for this and any corrective and preventive actions which he/she has taken to ensure that normal processes are adhered to as soon as possible. All protocol violations are entered directly into the eCRFs.

6.1 Medical History, Demographic and Other Baseline Information

The medical history comprises:

- General medical history
- Documentation of SLE diagnosis
- Historical medication therapy for SLE

The following demographic information will be recorded:

- Age
- Ethnic origin (Hispanic/Latino or not Hispanic/not Latino)
- Race (White, American Indian/Alaska Native, Asian, Native Hawaiian or other Pacific Islander, Black/African American)
- Height (without shoes, in cm)
- Body weight, without shoes (kg)
- Body mass index (BMI [kg/m²])

Other baseline characteristics will be recorded as follows:

- Concomitant medication documentation (see [Section 4.6](#))
- Status of child bearing potential and contraception

6.2 Safety Assessments

6.2.1 Laboratory Assessments

Laboratory tests will be performed at times defined in the Schedule of Assessments ([Section 3.4](#)). Patient eligibility will be determined based on these tests at screening. Unscheduled clinical labs may be obtained at any time during the study to assess any perceived safety concerns.

A central laboratory will be used (with the exception of urine pregnancy tests) to ensure accuracy and consistency in test results. Laboratory/analyte results that could unblind the study (ie, biomarker results) will not be reported to investigative sites. Urinalysis will be performed on midstream, clean catch specimens. Some biomarkers listed above will not be drawn at some sites due to geographical logistical challenges. See the laboratory manual for details.

Endpoint analyses will be based on changes from baseline assessments at Days 120 and 210.

Table 3. Laboratory Tests

Hematology	Chemistry	Urinalysis	Other Safety Tests
Hemoglobin	BUN	pH	Spot urine for protein/creatinine ratio
Hematocrit	Creatinine	Glucose (qual)	FSH ^b
RBC count	Glucose (fasting)	Protein (qual)	Urine pregnancy test ^c
RDW	Calcium	Blood (qual)	QuantiFERON [®] -TB Gold In-Tube test

Table 3. Laboratory Tests

Hematology	Chemistry	Urinalysis	Other Safety Tests
MCV	Sodium	Ketones	(QFT-G) ^d
MCH	Potassium	Nitrites	Serology ^d (Hepatitis B and C; HIV-1/2 combination)
MCHC	Chloride	Leukocyte esterase	Stool sample ^e
Platelet count	Total CO ₂ (bicarbonate)	Urobilinogen	Serum pregnancy test
WBC count	AST, ALT	Urine bilirubin	
CD4+ count	Total bilirubin	Microscopy ^a	
Total neutrophils (Abs)	Alkaline phosphatase		
Eosinophils (Abs)	Creatine kinase		
Monocytes (Abs)	Uric acid		
Basophils (Abs)	Albumin		
Lymphocytes (Abs)	Total cholesterol (fasting)		
	LDL-C (fasting)		
	HDL-C (fasting)		
	Triglycerides (fasting)		
	Total protein		
	PT/INR		

Additional Tests ^f (potential Hy's Law)	Immunogenicity, PD and other Biomarker Tests
AST, ALT (repeat)	ADA
Total bilirubin (repeat)	nAb ^g
Albumin (repeat)	pSTAT3 (predose [trough] samples only in Phase 1b)
Alkaline phosphatase (repeat)	Total IgG & IgM
Direct bilirubin	Plasma CCI
Indirect bilirubin	Plasma CCI & CCI
GGT	Whole blood for leukocyte immunophenotype
Prothrombin time/international normalized ratio (repeat)	CCI
Creatine kinase (repeat)	CCI
	CCI
	CRP
	Direct Coomb's test ^h

Abbreviations: Abs = absolute; ADA = anti-drug antibody; ALT = alanine aminotransferase; CCI; CCI; AST = aspartate aminotransferase; BUN = blood urea nitrogen; C = complement; CD4+ = cluster of differentiation 4; CRP = C-reactive protein; dsDNA = double-stranded deoxyribonucleic acid;; FSH = follicle stimulating hormone; GGT = gamma-glutamyltransferase; HDL-C = high-density lipoprotein cholesterol; HIV = human immunodeficiency virus; IgG = immunoglobulin G; IgM = immunoglobulin M; INR = international normalized ratio; IL-21 = interleukin 21; LDL-C = low-density lipoprotein cholesterol; MCH = mean corpuscular hemoglobin; MCHC = mean corpuscular hemoglobin concentration; MCV = Mean corpuscular volume; nAb = neutralizing antibody; pSTAT3 = phosphorylated signal transducer and activator of transcription 3; PT = prothrombin time; qual = qualitative; RBC = red blood cell; RDW = RBC distribution width; SAE = serious adverse event; SC = subcutaneous; CCI; TB = tuberculosis.

- a. On all urine samples.
- b. At screening only, in women who are amenorrheic for at least 12 consecutive months and under 55 years old.
- c. For WOCBP.

Table 3. Laboratory Tests

Hematology	Chemistry	Urinalysis	Other Safety Tests
d.	Screening only.		
e.	At screening, and if a patient develops diarrhea during the study a stool sample must be provided to test for ova, parasites, and cryptosporidium.		
f.	Additional testing for potential Hy's Law cases only (See Section 6.2.2.6.3).		
g.	If patient is positive for ADA.		
h.	If clinically indicated for hemolytic anemia.		

